7.1. Primary Endpoints

Defibrillator Cohort (including ICD and CRT-D Cohorts):

- Composite rate of first appropriately treated ventricular arrhythmia (by ATP or shock) or life-threatening symptoms associated to ventricular arrhythmia (defined as hemodynamic instability which requires treatment), whichever comes first under MADIT Arm B or C programming conditions in a study population with a majority of Japanese subjects

PM/CRT-P Cohort:

- All-cause mortality in subjects with a maximum of 3 risk factors (analyzed for MADIT II data⁷)

Non-device Cohort (ESC Guideline 2016 Indicated but not implanted subjects):

- All-cause mortality in the subject cohort with 2 to 5 predefined SCD driving risk factors

7.2. Secondary Endpoints

- All-cause mortality rate for subjects implanted with ICD/CRT-D (= ICD cohort plus CRT-D cohort = defibrillator cohort)

- Composite rate of HF events in ICD, CRT-D, and PM/CRT-P cohorts, which require IV treatment, HF related hospitalization, or led to HF death
- Therapeutic sustainability at 1 year in ICD, CRT-D, and PM/CRT-P cohorts, defined as free of qualified serious adverse device events (SADEs) post successful implantation in comparison to data from MADIT CRT, MADIT RIT, Optimind and Rally X4 studies
Examples for qualified SADEs: re-implant procedure, required invasive procedure related to the device system, pacing exit block, all-cause infection, and death due to therapy failure.
- Comparison of rate of sudden cardiac death in the non-device cohort with the rate of appropriately treated ventricular arrhythmias or sudden cardiac death in subjects implanted with ICD-CRT-D (defibrillator cohort)

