7.3. Additional Endpoints

The ancillary assessments will include:

- Subject medical assessment collected pre-enrolment (post implant) and at Close-out:
 - NYHA functional classification
 - LVEF
 - QRS duration
 - Physician's judgment on therapy outcome
 - Body mass index (BMI)
 - Diabetes mellitus type I and II
- Cross-over in device therapies
- Cause of death (SCD, Cardiac related, other reasons, unknown)
- Incidence and development of Atrial fibrillation in different patient cohorts during the cause of the study
- Impact of gender and age
- Magnetic resonance imaging (MRI) observations in association with reported clinical events
- Analysis of device data coming from Latitude data reports
- Health care utilization under Latitude
- Standard biomarkers for heart failure and other morbidities

8. Study Design

This is a prospective, non-randomized, multicenter, multi-cohort clinical outcome registry study to evaluate SOC. Neither the devices nor the implant procedure are part of this study.

Subjects will be implanted with the device per SOC within 0 to 45 days prior to enrolment in this study.

The decision as to which subject gets which device is made by the implanting physician and is not part of this study. In addition, subjects with specified risk factors (Section 9.2.5) and with no device will also be enrolled.

Devices must be programmed (considered a non-invasive procedure and SOC operation of the device) per protocol and according to the respective BSC IFU, and must be connected to the Latitude system for the duration of the trial. If this is not possible, a deviation will be recorded.

The Latitude database will be reviewed by the BSC Latitude team on regular basis for all study subjects and inconsistencies will be discussed with the study data management.

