9.3.1. General Exclusion Criteria

Subjects who meet any one of the following criteria (Table 9.3-1) are not allowed to be included in this clinical study. The exclusion criteria apply only at the time of enrolment into the study.

Table 9.3-1: General Exclusion Criteria

1. Subject is enrolled in any other concurrent study without prior written approval from BSC, with the exception of local mandatory governmental registries and observational studies/registries that are not in conflict and do not affect the following:
 - Schedule of procedures for the HINODE Study (i.e. should not cause additional or missed visits)
 - HINODE Study outcome
 - Conduct of the HINODE Study per Good Clinical Practice (GCP)/ International Standard Organization (ISO) 14155:2011/local regulations as applicable
2. Device implant revision is scheduled due to unstable result of an implant <45 days prior enrolment
3. Subjects with more than 5 of the following risk factors: LVEF \leq 35%, NYHA Class III or IV, LBBB with QRS 130 ms or QRS $>$ 150 ms, renal dysfunction (chronically BUN $>$ 26 mg/dL / $>$ 9.28 mmol/L), diabetes type I and II, chronic atrial fibrillation (permanent or persistent according to ESC Guideline 2016¹¹), prior MI, age $>$ 70 years, smoking today or during last 5 years
4. Subjects with chronic renal disease with chronic BUN \geq 50mg/dL or creatinine \geq 2.5 mg/dL
5. Subjects with coronary artery bypass graft (CABG) surgery or percutaneous coronary intervention (PCI) within the past three calendar months prior to enrollment
6. Subjects with enzyme-positive myocardial infarction within the past three calendar months prior to enrollment
7. Subjects who are expected to survive for <1 year with good functional status
8. Subject's physician does not allow participation
9. Subject is not willing and capable of participating in all testing or visits associated with this clinical study at an approved clinical study center and at the intervals defined by this CIP
10. Unwilling to sign the consent for participation
11. Women of childbearing potential who are or might be pregnant at the time of study enrolment
12. ICD and CRT-D cohorts: implanted with a non-BSC device system. PM/CRT-P cohorts: implanted with a non-BSC PG device.

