10.1. Point of Enrolment

Subjects will only be enrolled in this registry study if they meet all eligibility criteria and provide written informed consent. If a subject is found not to meet all applicable eligibility criteria, the subject will be withdrawn from the study; any points of ineligibility must be clearly documented in the enrolment/screening log. These subjects will be considered

consent ineligible as discussed in Section 10.3, and will not count towards the enrolment ceiling. Any subject that signs consent and meets all inclusion criteria and does not meet any Exclusion Criteria will be enrolled in the study. Any reportable events, as defined in Section 20 of this CIP, must be collected after written informed consent is obtained.

Subjects enrolled under protocol version C deviating from eligibility criteria of protocol version D will be withdrawn from the study. Other subjects previously not meeting eligibility criteria of protocol version C, but now meeting eligibility criteria of protocol version D, will be accepted under protocol version D and no protocol deviation will need to be documented in the eCRF.

10.2. *Withdrawal*

All subjects enrolled in this registry study (including those withdrawn from the clinical study or lost to follow-up) shall be accounted for and documented. If a subject withdraws from the study, the reason(s) shall be reported. If such withdrawal is due to problems related to investigational device safety or performance, the investigator shall ask for the subject's permission to follow his/her status/condition outside of the clinical study.

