11.5. Six-monthly Visit

Subjects will be visited every 6 months from enrolment (Day 0) until Close-out Visit. During the 6-monthly follow-up visit, device assessment/interrogation should be performed according to SOC practices. Details on the occurrence of any adverse device effects (ADEs), SAEs, SADEs, and device deficiency (DD), which have occurred since enrolment (Day 0), are to be recorded.

Echocardiography or equivalent method according to center's SOC will be used to determine basic measures: LVEF, diastolic diameters, and volumes. If the echo is not done per SOC, no deviation will be recorded.

Data on actual number of MRI scans performed according to center's SOC since the enrolment, including information about scanned body parts, reason for scan, etc., will be collected.

Subjects will have their device performance, all Latitude alerts on. Latitude report is requested every 14 days, and diagnostic data are downloaded remotely by the Latitude BSC team as Latitude report during this visit timeframe.

Latitude remote device interrogation is requested to be programmed every 2 weeks or more frequent.

Subjects that receive re-implant, repositioning, device upgrade or new device implant post enrolment, as determined by the investigator, will continue to follow same initial procedures and schedules as described for Day 0 at the initial enrolment. The reason for re-implant/revision is to be documented as an Adverse Event in the eCRF.

Physician's judgment on therapy and risk factor assessment will be collected on standard follow-up CRF as planned at enrolment. In addition to the Re-implant CRF, the form for unscheduled visits will be used for event reporting.

If there were any protocol deviations since the last study visit, they have to be recorded.

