Serious Adverse Device Effect (SADE) Ref: ISO 14155 Ref: MEDDEV 2.7/4	Adverse device effect that has resulted in any of the consequences characteristic of a serious adverse event.
Unanticipated Adverse Device Effect (UADE) Ref: 21 CFR Part 812	Any serious adverse effect on health or safety or any life-threatening problem or death caused by, or associated with, a device, if that effect, problem, or death was not previously identified in nature, severity, or degree of incidence in the investigational plan or application (including a supplementary plan or application), or any other unanticipated serious problem associated with a device that relates to the rights, safety, or welfare of subjects.
Unanticipated Serious Adverse Device Effect (USADE) Ref: ISO 14155 Ref: MEDDEV 2.7/4	Serious adverse device effect which by its nature, incidence, severity, or outcome has not been identified in the current version of the risk analysis report. NOTE 1: Anticipated serious adverse device effect (ASADE) is an effect which by its nature, incidence, severity or outcome has been identified in the risk analysis report.
Device Deficiency Ref: ISO 14155 Ref: MEDDEV 2.7/4	An inadequacy of an investigational medical device-related to its identity, quality, durability, reliability, safety or performance. This may include malfunctions, use error, or inadequacy in the information supplied by the manufacturer.

Abbreviations: ADE = Adverse Device Effect; AE = Adverse Event, ASADE = anticipated serious adverse device effect; EC=Ethics Committee; ISO = International Standard Organization, MEDDEV = medical device guidance; SAE = Serious Adverse Event; USADE = Unanticipated Serious Adverse Device Effect

Underlying diseases are not reported as AEs unless there is an increase in severity or frequency during the course of the investigation. Death should be recorded as an SAE, and should include a detailed description of circumstances and expected cause.

Any AE experienced by the study subject after informed consent, whether during or subsequent to the procedure, must be recorded in the eCRF.

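### The 1-year SADE-free endpoint is worded from implantation, but the plan states no route for collecting device events between implant and consent, a gap of up to 45 days

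*Combined protocol and SAP*

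**What the plan says.** Section 7.2 (also the synopsis and Section 12.1.5) gives the device cohorts a secondary endpoint of therapeutic sustainability at 1 year, "defined as free of qualified serious adverse device events (SADEs) post successful implantation". It adds: "Examples for qualified SADEs: re-implant procedure, required invasive procedure related to the device system, pacing exit block, all-cause infection, and death due to therapy failure". The rate is to be read "in comparison to data from MADIT CRT, MADIT RIT, Optimind and Rally X4 studies".

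On timing, Section 8 states: "Subjects will be implanted with the device per SOC within 0 to 45 days prior to enrolment in this study". Section 11.1 makes the consent signature the point of enrolment, and Section 11.4 has device subjects sign after a successful implant.

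On event collection:
- Section 20.2: "Any AE experienced by the study subject after informed consent, whether during or subsequent to the procedure, must be recorded in the eCRF". Section 20.1 likewise ties required recording to events after consent and enrolment.
- Section 10.1: reportable events "must be collected after written informed consent is obtained".
- Section 11.5: at the six-monthly visit, device effects and serious events "which have occurred since enrolment (Day 0), are to be recorded".
- Table 11.1-1: the adverse event assessment review is not required at enrolment. The next row, reporting of SAEs, SADEs, ADEs and device deficiencies, is required there.

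General exclusion 2 (Section 9.3.1) removes subjects for whom: "Device implant revision is scheduled due to unstable result of an implant <45 days prior enrolment". Section 12.1.5 calls the secondary analyses descriptive and exploratory and leaves their methods to an SAP.

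**The concern.** The endpoint is described from implantation, while the stated recording rules begin at consent. A subject whose pacing exit block was corrected on day 5 and who consents on day 30 has had an event of a listed type. The plan does not say that anyone should look for it. If it is not found, the subject counts as SADE-free.

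General exclusion 2 acts in the same direction on a different group: subjects with an unstable recent implant awaiting revision never enter the denominator. What is at stake is the meaning of the reported rate. It would look like freedom from qualified SADEs over a full post-implant year, and would be set beside four earlier studies on that footing, although part of the earliest period was not systematically observed.

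**Working it through.** The plan gives no expected SADE rate, sample size or power for this endpoint, so there is no figure to reproduce. The check compares the time windows and then illustrates the size.

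**Windows set side by side**
1. Endpoint: after successful implantation, to 1 year (Section 7.2). An implant origin also agrees with the device-cohort primary analyses, whose Kaplan-Meier curves start at implant (Sections 12.1.1.2, 12.1.2.2, 12.1.3.2).
2. Required recording: events after consent (Sections 20.1, 20.2).
3. Look-back at visits: to enrolment at the six-monthly visit (Section 11.5), and to the last visit at interim and close-out visits (Sections 11.7, 11.8). None reaches the implant.
4. Enrolment visit: SADE reporting is ticked in Table 11.1-1 without a look-back period. The protocol can state one when it wants to: Section 11.4 asks for the number of MRI scans since the implant procedure. It has no equivalent for SADEs.

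The uncovered share of the year is gap/365. It is 0% at a gap of 0 days, 22.5/365 = 6.2% at the midpoint, and 45/365 = 12.3% at the maximum.

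**Illustrative size**

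Let R be the true 1-year risk of a qualified SADE, f the share of those events in days 0 to 45, and s the share of those early events that fall before consent. If none of these is collected,

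reported SADE-free rate = 1 − R × (1 − f × s), and the upward bias is R × f × s.

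R, f and s are all assumptions. Taking s = 0.5 corresponds to consent and early events both spread evenly over days 0 to 45. If events fall closer to implant, s is larger. Taking s = 1 corresponds to everyone consenting on day 45.

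| R | f | s | Reported | True |
|---|---|---|---|---|
| 10% | 0.30 | 0.5 | 1 − 0.10 × 0.85 = 91.5% | 90% |
| 10% | 0.60 | 0.5 | 1 − 0.10 × 0.70 = 93.0% | 90% |
| 10% | 0.30 | 1 | 1 − 0.10 × 0.70 = 93.0% | 90% |
| 10% | 0.60 | 1 | 1 − 0.10 × 0.40 = 96.0% | 90% |

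The bias is therefore 1.5 to 6.0 points at R = 10%. Over the same f and s it is 0.75 to 3.0 points at R = 5% and 2.25 to 9.0 points at R = 15%. At the low end, a constant hazard with consent at day 7 gives f × s = 7/365 = 0.019 and a reported rate of 90.2% against 90%. Consent on the implant day gives no bias.

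In subjects, the device-cohort minimums are 117 + 95 + 172 = 384, and 384 × 10% = 38.4 would have a qualified SADE. Between 38.4 × 0.15 = 5.8 and 38.4 × 0.60 = 23.0 of them would be classed as event-free, provided none has a later qualified SADE. The effect of general exclusion 2 is not included and cannot be sized from the documents.

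**The case against.** Several points on the other side stand in whole or in part.

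- **Table 11.1-1.** A reader who looks only at the assessment-review row might infer that SADEs before consent are never recorded. The documents do not support that. The reporting row is ticked at enrolment, and at a visit where consent has just been signed there is little for it to capture except earlier events. What stands is a conflict with Sections 20.1 and 20.2 and no stated look-back.
- **Other traces.** Enrolment collects implant dates, device and lead details, previous systems and the physician's judgment on therapy, and implant procedure records are source documents (Sections 11.4, 11.9). A replaced generator or lead might show. An infection, or exit block corrected without new hardware, might not. None of these items is a SADE collection.
- **Section 10.1.** It might be read as barring earlier events. It says when collection takes place and not when the event must have begun, so the point rests on Sections 11.5, 20.1 and 20.2.
- **Time origin.** Only the wording of the definition gives it. The word successful could be meant to condition on a stable system, in which case general exclusion 2 partly defines the population. The plan does not say so, and the rate would then need that label.
- **Complication definitions.** A reader might point to perforation, pneumothorax or hematoma in Table 26.2-1 as the events lost. They are not among the listed examples of qualified SADEs. The table classes hematoma and pneumothorax needing invasive treatment as SAEs, and of these procedural complications only tamponade is called a SADE. Nothing in the documents gives their timing.
- **Comparison.** A reader might infer that the study would show falsely better results than the four earlier studies. The documents do not say when those studies began counting, so that remains conditional.

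**Conclusion.** The point holds in a limited form. Qualified SADEs between implant and consent lie inside the endpoint as worded but have no stated collection route, and the enrolment tick in Table 11.1-1 is not reconciled with Section 20. Missed early events and the exclusion of pending revisions can each only raise the SADE-free rate. Subjects who die before consent also cannot enter.

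The loss is partial: events after consent but still within 45 days of implant are captured. Its size cannot be derived from the documents. The 1.5 to 6 points rest wholly on the assumed 10% risk, the 30% to 60% early share and the consent pattern, and also on no earlier event being picked up at the enrolment visit. Because the endpoint is secondary and descriptive, no hypothesis test or sample size is affected. What is affected is how the rate is read and compared.

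**What to change.** Preferred: once consent is signed, abstract from the hospital chart and device record every qualified SADE from implant to consent and count it in the endpoint. State this look-back in Table 11.1-1 and in Section 20 so that the two agree. Doing it after signature respects the bar in Section 11.3 on study-specific collection before consent. Because subjects with a pending revision still do not enter, report the rate as conditional on a stable system at enrolment.

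Alternative: define the endpoint with delayed entry, so that each subject joins the risk set at consent on a time scale that starts at implant. The SAP must then say how a subject with a qualified SADE before consent is handled, or restate the endpoint as the first qualified SADE after enrolment.

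In either case, limit the comparison with the four earlier studies to the same post-implant window, and say so if their starting point cannot be established.

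The preferred change costs one chart-review item at a visit that already collects implant and device data, plus wording in the table, Section 20 and the SAP. The reported rate is likely to be less favourable.

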7.3. Additional Endpoints

The ancillary assessments will include:

- Subject medical assessment collected pre-enrolment (post implant) and at Close-out:
 - NYHA functional classification
 - LVEF
 - QRS duration
 - Physician's judgment on therapy outcome
 - Body mass index (BMI)
 - Diabetes mellitus type I and II
- Cross-over in device therapies
- Cause of death (SCD, Cardiac related, other reasons, unknown)
- Incidence and development of Atrial fibrillation in different patient cohorts during the cause of the study
- Impact of gender and age
- Magnetic resonance imaging (MRI) observations in association with reported clinical events
- Analysis of device data coming from Latitude data reports
- Health care utilization under Latitude
- Standard biomarkers for heart failure and other morbidities

8. Study Design

This is a prospective, non-randomized, multicenter, multi-cohort clinical outcome registry study to evaluate SOC. Neither the devices nor the implant procedure are part of this study.

Subjects will be implanted with the device per SOC within 0 to 45 days prior to enrolment in this study.

The decision as to which subject gets which device is made by the implanting physician and is not part of this study. In addition, subjects with specified risk factors (Section 9.2.5) and with no device will also be enrolled.

Devices must be programmed (considered a non-invasive procedure and SOC operation of the device) per protocol and according to the respective BSC IFU, and must be connected to the Latitude system for the duration of the trial. If this is not possible, a deviation will be recorded.

The Latitude database will be reviewed by the BSC Latitude team on regular basis for all study subjects and inconsistencies will be discussed with the study data management.

8.1. Scale and Duration

As soon as a minimum of 556 eligible subjects are entered into the study database, the closure of enrolment can begin. After closure of enrolment, sites must obtain approval from the sponsor or the sponsor's delegated representative for all remaining subjects who are consented but who are not yet enrolled into the study database. The maximum number of followed study subjects is 950. Since this is an event dependent analysis, the total number of subjects might be considerably lowered in all different cohorts, depending on actual number of events. It would allow for an early closure of the study enrollment.

Approximately 40 investigational sites in Japan will be included. If a site does not enroll a sub

ject within a 3-month time period, the site may be closed for enrolment and replaced at the discretion of the sponsor.

Enrolment is expected to take approximately 18 months. The total study duration with all follow-up data collected will take up to 50 months. All subjects will remain in the study until the last subject completes his/her last visit. The maximum study duration for any subject will be 34 months (first subject first visit [FSFV] to last subject last visit [LSLV]); the minimum study duration will be the time of enrolment of the last subject enrolled (last subject first visit [LSFV] to LSLV) and is expected to be 16 months. Study completion and data analysis are anticipated in 2020.

Figure 8.1-1: HINODE Study Design

TIME AXIS	PERIOD OF ENROLMENT OF SUBJECTS				1-YEAR FOLLOW-UP FOR ALL SUBJECTS ENROLLED		CLOSE OUT VISIT
	6 months	6 months	6 months	6 months	6 months	6 months	
FIRST SUBJECT	Device implant or no device*	EV Day 0	1st 6-monthly visit			5th 6-monthly visit	2 months before** LSLV until 4 months LSLV
FURTHER SUBJECTS	Device implant or no device*	EV Day 0	1st 6-monthly visit			4th 6-monthly visit	
FURTHER SUBJECTS	Device implant or no device*	EV Day 0	1st 6-monthly visit			3rd 6-monthly visit	
LAST SUBJECT	Device implant or no device*	EV Day 0			2 nd 6-monthly visit = COV = LSLV ***		

* device is BSC device, either ICD or CRT-D or CRT-P or PM; no device = no device implanted, but indicated according to ESC Guideline 2016

** if COV is done within 2 months before LSLV, the COV replaces the last 6-monthly visit

*** LSLV will be conducted within 12 months + 60 days post enrollment

Abbreviations: COV = Close out visit; EV = Enrolment visit; LSLV = last subject's last visit

8.2. *Treatment Assignment*

This is a non-randomized prospective registry study to collect clinical data in the real-life setting in Japan. Enrolled subjects will include those who have been implanted with BSC pacing or defibrillation devices as well as post MI subjects with preserved EF and no device treatment. Subjects will be assigned to one of the 3 following Subject Cohorts according to device implanted:

1. ICD: 117 to 270 subjects
2. CRT-D: 95 to 250 subjects
3. PM/CRT-P: 172 to 200 subjects

A fourth cohort of non-implanted subjects will also be enrolled:

4. Non-device 172 to 300 subjects
(ESC Guideline 2016 Indicated but not implanted)

8.3. *Justification for the Study Design*

The primary objective of this study is to collect clinical event data for selected patient cohorts who are at risk of ventricular tachy-arrhythmias and HF events. In order to obtain “real world” data, the study inclusion/exclusion criteria and follow-up schedule have been written generally enough to allow for study site specific SOC which should accurately capture the clinical data in a “standard” clinical setting. Additionally, by requiring study sites to follow their specific SOC, risk to the subject is minimized because the treatment received by the subject will be similar to the treatment the subject would receive if not participating in the study.

Requiring that all implanted devices be programmed per protocol and the respective BSC IFU, all devices must be intended to be connected to the Latitude system during study duration.

The determination of sample size is provided in Section 12.1.6.

9. Subject Selection

9.1. *Study Population and Eligibility*

Inclusion and exclusion criteria are listed in Sections 9.2 and 9.3 below.

Subjects who are enrolled but later determined to not fulfil all inclusion and exclusion criteria at the time of enrolment will be considered to have incurred a Clinical Investigation Plan (CIP) deviation. These subjects will be withdrawn from the study immediately and will not be included in the planned data analysis.

9.2. *Inclusion Criteria*

All inclusion criteria apply only at the time of enrolment into the study.

If a subject's medical conditions change after inclusion into the study so that one or several of the general inclusion criteria and inclusion criteria of the pertinent cohort are no longer met, the subject remains in the study.

If it turns out after enrolment into the study that one or several of the general inclusion criteria and inclusion criteria of the pertinent cohort were violated at the time of enrolment into the study, the study has to be ended in this subject.

